14.3.2 Other safety analyses

The absolute and relative frequencies for subjects with a given TEAE with respect to the preferred term according to the latest available version of the MedDRA, as well as the absolute frequencies of the individual TEAEs that have occurred, will be determined within each system organ class. Additional tables will summarize TEAEs by maximum intensity and causal relationship with UCB7665, as judged by the investigator. Adverse events will be categorized by severity according to the CTCAE version 4.03 grading. In case the CTCAE grading is not available, the intensity (mild/moderate/severe) will be utilized. For the purpose of the tabulations CTCAE grades will be aligned with the intensity classifications (mild/moderate/severe) to enable pooling of the AEs in the summaries. The TEAEs leading to discontinuation of IMP and treatment-emergent SAEs will also be summarized. The action taken, time of onset relative to dosing, and duration of each AE will be listed only.

For the continuous laboratory variables, the values and changes from Baseline will be summarized at each time point. For categorized values according to the reference range, shift tables from Baseline to each post-Baseline time point will be presented for selected variables to be defined in the SAP. Values outside the reference range will be flagged in the data listings. The number and percentage of subjects with markedly abnormal laboratory results (based on CTCAE grading) will be tabulated for each dose arm.

Normal versus abnormal findings with regard to the various ECG parameters and the overall ECG will be analyzed as required. The focus of the 12-lead ECG analysis will be the identification of outliers and of any trends for changes following administration of UCB7665 with respect to QT/QTc. Descriptive statistics will be presented for ECG value and changes from Baseline over time based on the mean of the triplicate assessments at each time point.

Descriptive statistics will be reported for all vital sign measurements (including systolic and diastolic blood pressure, pulse rate, temperature, and respiratory rate). Measured values and changes from Baseline will be summarized by time point.

Physical examination findings and the results of any pregnancy testing will be presented in listings only.

Safety analyses will be presented by dose arm.

14.4 Planned efficacy and other analyses

The main efficacy variable is the maximum increase from Baseline in platelet count during the study. The maximum increase from Baseline and maximum platelet count during the study will be summarized by dose arm.

In addition, all measurements of platelet count will be summarized by dose arm and time point using descriptive statistics (including changes from Baseline).

For dose arms with ≥10 subjects, a 1-sided t-test will be applied to assess if the average maximum increase from Baseline is greater than zero. In case the assumptions for the-t-test are not fulfilled, an alternative nonparametric method may be considered. Further details will be

provided in the SAP. The Response, Complete Response, and platelet count $\geq 50 \times 10^9 / L$ will be summarized (number of subjects and percentages) and presented with 90% 2-sided confidence intervals for the rate of responders at each time point and overall (across all time points). Response and Complete Response are defined in Section 4.2.2. The analysis will be repeated for the Clinical Response variables defined in Section 4.2.2.

Time to Response, time to Complete Response, time to platelet count $\geq 50 \times 10^9 / L$, duration of Response, duration of Complete Response, duration of platelet count $\geq 50 \times 10^9 / L$, and Baseline-corrected AUEC for platelet count will be calculated and summarized by dose arm. The time to first response will be analyzed using a log-rank test and displayed using Kaplan-Meier curves. The time to Response, time to Complete Response, and respective durations will be summarized by dose arm.

The results from the ITP bleeding scale will be summarized at each time point and will include the grades for each of the 3 major domains: skin (S), visible mucosae (M), and organs (O). In addition the number and percentage of subjects with severe or clinically relevant bleeding and number and percentage of subjects with absence of bleeding will be summarized at each time point.

Results of the NFI-MS will be summarized at each time point, using summary scores where applicable. Changes from Baseline will be calculated and summarized.

Additional subgroup analyses may be performed as needed and further details will be provided in SAP regarding these analyses.

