In summary, the genetic, epigenetic, and genomic elements of ITP are complex and require further elucidation to understand the cause, progression, and appropriate treatment of ITP. Through the voluntary collection of blood DNA/and RNA samples from consenting subjects, this substudy will help enable further investigation of this complex disease.

SELECTION AND WITHDRAWAL OF SUBJECTS

Inclusion criteria

To be eligible to participate in this study, all of the following criteria must be met:

1. An Institutional Review Board (IRB)/Independent Ethics Committee (IEC) approved written Informed Consent form is signed and dated by the subject.

Confidential Page 58 of 353

- 2. Subject is considered reliable and capable of adhering to the protocol, visit schedule, or medication intake according to the judgment of the investigator.
- 3. Subject is male or female, ≥ 18 years of age at Visit 1 (Screening).
- 4. Subject has a diagnosis of primary ITP for a minimum of 3 months prior to Screening Visit.
- Measured as follows: At Screening Visit, 2 separate blood collections for platelet count to be performed on the same day with at least 1 value below $30x10^9/L$ and both values below $35x10^9/L$. At Baseline Visit (Visit 2), a platelet measure will be tell should be below $35x10^9/L$. 5. Subject has a platelet count $<30\times10^9$ /L at Screening and $<35\times10^9$ /L at Baseline (Visit 2).
- 6. Subject has a current or history of a peripheral blood smear consistent with ITP (thrombocytopenia with normal size or only slightly enlarged platelets and normal red and white blood cell morphology).
- 7. Female subjects of childbearing potential must have a negative serum pregnancy test at the Screening Visit, which is confirmed to be negative by urine testing prior to the first dose of IMP at Week 1 (Visit 2) and prior to further dosing at each study visit thereafter.
 - Female subjects of childbearing potential must agree to use a highly effective method of birth control, during the study and for a period of 2 months after their final dose of IMP. Highly effective forms of birth control are methods which achieve a failure rate of less than 1% per year when used consistently and correctly. Highly effective methods of birth control include:

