14.8 Determination of sample size

The sample size of 15 subjects in Dose Arms 1 and 2, is mainly based on the efficacy objective of the study. In addition the 15 subjects in Dose Arms 1 and 2 ensure that sufficient data are available to form conclusions about the safety of administering UCB7665. Based on the safety data from dose arms 1 and 2, the sample size of 6 to 12 subjects in Dose Arms 3, 4 and 5 is judged to be sufficient in order to explore subjects' safety and IgG reductions under different dose regimens and is not based on a formal sample size calculation.

For Dose Arms 1 and 2, an approximate sample size calculation for the efficacy variable "maximum increase from Baseline in platelet count" shows that 15 subjects would be sufficient to show a change from Baseline with 1-sided testing at 5% and power of 80%. The anticipated change is based on an assumed Baseline average of $25 \times 10^9 / L$ and a clinically meaningful maximum value of $100 \times 10^9 / L$. The calculation made use of platelet count data presented in a publication by Robak T (Robak et al, 2009), but it is approximate as maximum changes from Baseline for individual subjects were not available, necessitating the use of the maximum average platelet count instead. The SD is taken from visual inspection.

With 15 subjects, the responder endpoints will confirm a true 50% response rate, in excess of the maximum 15% anticipated with no treatment benefit, with power in excess of 80%.

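### The t-test on the main efficacy variable compares each subject's highest of 8 to 13 platelet counts with one Baseline count, so its null value of zero is wrong even for an inactive drug

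*Protocol*

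**What the plan says.** Section 14.4 states: "The main efficacy variable is the maximum increase from Baseline in platelet count during the study". The test is specified as follows: "For dose arms with ≥10 subjects", "a 1-sided t-test will be applied to assess if the average maximum increase from Baseline is greater than zero". If the t-test assumptions fail, a nonparametric method may replace it. No other null value is given.

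Section 14.8 sizes Dose Arms 1 and 2 mainly on this variable: "15 subjects would be sufficient to show a change from Baseline with 1-sided testing at 5% and power of 80" per cent. The planned change is from an average of 25 to a maximum of 100 (x10^9/L). The SD was read by eye from a publication and is not stated.

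Baseline is the last non-missing value before the first dose (Section 14.2). Platelets are drawn with each safety laboratory sample and analysed centrally (Section 9.1). Tables 5-1 to 5-5 schedule those samples at every visit after Baseline. Entry requires low counts. Criterion 5 of Section 6.1 asks for "2 separate blood collections for platelet count to be performed on the same day" at Screening, both below 35 and at least one below 30, and for a local count below 35 at Visit 2.

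Section 14.4 also plans a log-rank test of time to first response, and responder rates with 90% confidence intervals. Section 14.8 plans the responder endpoints as a true 50% against at most 15% without treatment benefit.

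**The concern.** A test of a mean against zero has its stated level only if the mean is zero when the drug does nothing. Here each subject has many chances to exceed a single reference value, and only the best one counts. Entry on a low count pushes the same way, because later counts tend to drift back up. There is no untreated arm to absorb either effect.

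At stake is the reading of the result. A significant p-value at a nominal 5% would be taken as evidence that platelets rose because of the drug, when an inactive drug would give almost the same p-value. The large planned change of 75 does not help, since the test cannot separate a large effect from ordinary fluctuation.

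**Working it through.** **Inputs from the protocol.** Section 14.4: 1-sided one-sample t-test, null mean 0, arms with at least 10 subjects. Section 14.8: n = 15, 1-sided 5%, power 80%, change 100 − 25 = 75. Post-Baseline counts k from Tables 5-1 to 5-5: Arm 1, Visits 3 to 15, k = 13; Arm 2, Visits 3 to 13, k = 11; Arm 3, Visits 3 to 12, k = 10; Arms 4 and 5, Visits 3 to 10, k = 8.

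**Inputs not in the protocol, assumed and varied.** Within-subject correlation 0 to 0.95; normal or lognormal counts (median 18); log-SD 0.4, or 0.3 to 0.7 where the entry limits were applied.

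**Step 1: the plan's own figures.**
- *Continuous variable.* The 15 subjects cannot be reproduced without an SD. Solving backwards with the noncentral t, n = 15 at 1-sided 5% and 80% power needs a standardised change of 0.675, so SD = 75 / 0.675 ≈ 111. The normal approximation gives (1.645 + 0.842)/√15 = 0.642, so SD ≈ 117. Power is 87% at SD 100 and 74% at SD 120.
- *Responders.* A rule of at least 6 of 15 has exact 1-sided alpha 1.7% at a 15% rate and power 84.9% at 50%. At least 5 of 15 gives alpha 6.2%. The claim of more than 80% power reproduces.

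**Step 2: the mean under no drug effect.** If the Baseline count and the k later counts are exchangeable, the chance that the maximum exceeds Baseline is k/(k+1):
- k = 13: 13/14 = 93%
- k = 11: 11/12 = 92%
- k = 10: 10/11 = 91%
- k = 8: 8/9 = 89%
- k = 1: 1/2 = 50%

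For normal counts with SD σ and correlation ρ, the mean of (maximum − Baseline) is σ·√(1−ρ)·E(k), where E(k) is the expected maximum of k standard normals: 1.67 for k = 13 and 1.42 for k = 8. With k = 13 and ρ = 0.8 this is 0.447 × 1.67 ≈ 0.75σ. It is above zero for every ρ below 1.

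**Step 3: rejection rate of the planned test with no drug effect** (simulation; nominal level 5%):

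| Arm size, counts | Exchangeable normal | Exchangeable lognormal | Autocorrelated normal | Lognormal, entry limits applied |
|---|---|---|---|---|
| n = 15, k = 13 | 100% | 100% | 100% | 100% |
| n = 15, k = 11 | 100% | 100% | 99–100% | not run |
| n = 10, k = 10 | 99% | 96–97% | 92–99% | not run |
| n = 10, k = 8 | 97% | 94–95% | 87–97% | 96–99% |

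With the entry limits applied, the mean maximum increase of an inactive drug was 3 to 22 x10^9/L for k = 13. A further set of runs (within-subject CV 10 to 50%) gave 84 to 99% for n = 10 and 90 to 100% for n = 12, both with k = 8.

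**Step 4: contrast.** The same t-test at one fixed post-Baseline visit (k = 1, n = 15, no selection) rejects in 4.9%. With selection on low counts it rejects in 4 to 17%; the excess over 5% is regression to the mean.

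**The case against.** Several stronger conclusions are tempting, and the protocol does not support them.

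- *That this is the only efficacy test or the only formal efficacy evidence.* Section 14.4 also has the log-rank test and the responder intervals, and Section 14.8 sets the responder rate against an explicit no-benefit rate. The log-rank test gives limited help, because without an untreated arm it can only compare dose arms. The responder comparison does address drug effect.
- *That Section 14.4 promises a 5% level.* It names none. The level appears in Section 14.8, in the planning of Arms 1 and 2.
- *That the 80% power is false.* It cannot be checked without the SD, but nothing shows it to be wrong. A null value set too low does not reduce the chance of rejection.
- *That eligibility selects directly on the analysis Baseline.* Sections 8.2.1 and 12.7 split the Visit 2 sample: the local result decides entry, and the other sample goes to the central laboratory. This removes independent laboratory error from that selection step. Same-day biological fluctuation remains, as does selection at Screening.
- *That all five arms are affected.* Arms 3 to 5 grow from 6 to 12 subjects in steps of three (Section 5.1), so they reach the threshold of 10 only if enlarged to 12.

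The best defence is that safety is the primary objective (Section 3.1) and that opening, stopping and enlarging arms rest on safety review (Sections 5.1 and 14.7). That stands, and it limits the severity. It does not repair the test. Nor does the reference to further details in the SAP, because the variable and the null are fixed in the protocol.

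**Conclusion.** The point holds for the test as specified. Zero is the wrong null for a maximum increase, and the 1-sided 5% level planned for Arms 1 and 2 does not hold. That the mean under no effect is positive follows from the definition of the variable and needs no assumption beyond some within-subject fluctuation. The size rests on assumed variability and correlation: about 99 to 100% false rejection in Arms 1 and 2, and roughly 84 to 100% in Arms 3 to 5 if they are tested. These ranges belong to the scenarios run and are not bounds. Stronger persistence between visits combined with more skewness lowers them somewhat in small arms, but nowhere near 5%.

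Severity: should be fixed. Change in platelet count is a secondary objective (Section 3.2), and no dose-arm decision in the protocol depends on this p-value. The harm is to the interpretation of the efficacy result.

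**What to change.** Report the maximum value and the maximum increase descriptively, with no test against zero. Then choose one of two routes for the formal statement:

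1. Apply the 1-sided 5% test to the change from Baseline at one pre-specified visit common to all arms, for example 7 days after the last dose (Visit 9, 7, 6 and 4 in Arms 1, 2, 3 and 4/5). The study day of that visit differs by arm (36, 22, 15 and 8).
2. Base the efficacy claim on the responder rate against the stated 15%, and say whether the 15% refers to response at least once during the study or at a given visit.

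Restate the sample-size sentence in Section 14.8 for the chosen variable, giving the SD if it is continuous. Acknowledge that some regression to the mean remains in any uncontrolled change from Baseline, reduced but not removed by the separate local and central samples at Visit 2.

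The cost is protocol and SAP wording and one recalculation, with no new data. The drawback of the first route is that a brief peak outside the chosen visit would be seen only in the descriptive summary.

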14.4.2 Pharmacokinetic analyses

Pharmacokinetic variables of UCB7665 (eg, like AUC, C_{max}) cannot be derived, since blood sampling will be performed at 1 time point per visit only. Thus, PK is restricted to concentration data.

Individual concentrations of UCB7665 data will be summarized using the number of available observations, mean, median, SD, minimum, maximum, geometric mean, and geometric coefficient of variation (assuming log normally distributed data). Values below the lower limit of quantification (LLOQ) will be reported with a clear sign indicating that they were below the LLOQ. Descriptive statistics of concentrations will be calculated if at least two thirds of the individual data points are quantifiable (≥LLOQ). Individual concentrations of UCB7665 will also be displayed graphically.

Population PK analyses and PK/PD analyses may be conducted for the PD variables of interest. All such PK and PK/PD analyses will be described in a separate Data Analysis Plan; however, results will not be reported in the Clinical Study Report.

14.4.3 Pharmacodynamic analyses

For all PD variables, descriptive statistics for the values and change from Baseline and/or percentage change from Baseline will be tabulated by time point.

The PD variables will include ITP-specific autoantibodies total IgG, and IgG subclasses. In addition, for total IgG, the maximum decrease from Baseline and minimum value will be evaluated and summarized. Figures of mean values over time and changes from Baseline will be presented.

14.4.4 Immunologic variables

All immunologic variables including concentrations of immunoglobulins (IgA, IgE, and IgM), serum (C3 and C4) and plasma (C3a and C5a) complement levels, serum BAFF levels, and lymphocyte counts (B and T) will be summarized by dose arm over time (including changes from Baseline) using descriptive statistics. Figures of mean values over time and changes from Baseline may be presented.

The ADA status (negative/positive) will be summarized by dose arm at each visit and overall; figures will also be presented in conjunction with PK concentrations of UCB7665.

The results of any cytokine analyses (for subjects who experience infusion reactions) will be wind any extension summarized if appropriate.

Further details will be provided in the SAP.

14.4.5 Other analyses

14.4.5.1 Subject disposition

The number of subjects who were screened, dosed and completed/prematurely discontinued the study, as well as the reason for discontinuation, will be presented using frequency counts and percentages.

14.4.5.2 Subject characteristics

Summaries of the following will be provided:

- Demographics (including gender, age, height, weight, body mass index)
- Medical history
- Past, prior, and concomitant medications

Concomitant medical procedures will be listed only.

14.4.5.3 Baseline disease characteristics

Summaries of the following will be provided:

- Baseline disease characteristics (including disease duration)
- Baseline values of the immunological parameters (IgG, IgM, IgA, IgE, lymphocytes [B and T])
- ITP-specific antibodies
- Serum complement levels (C3 and C4) and plasma complement levels (C3a and C5a)

Subject exit interview 14.4.5.4

në res Report. The results of the exit interview will be reported by UCB and separate to the Clinical Study

Handling of protocol deviations

Important protocol deviations are identified as part of the data cleaning process in the Data Cleaning Plan (DCP). Ongoing data cleaning meetings will be held throughout the duration of the study. Objectives of these meetings include to review and update (if necessary) the important protocol deviations in the DCP and discuss exclusion of subjects from analysis populations. Furthermore, overall trends in protocol deviations will be discussed at the Data Evaluation Sor variations thereof Meeting. Through this ongoing data cleaning and evaluation process, all decisions regarding important protocol deviations and exclusions from analysis populations are made on an ongoing basis.

14.6 Handling of dropouts or missing data

All imputation of missing or partial dates for safety assessments, as well as handling missing efficacy data (where applicable), will be detailed in the SAP.

14.7 Planned interim analysis and data monitoring

A DMC will be convened to monitor emergent safety data during the study. The DMC will comprise at least 1 external expert, the UCB study physician, the UCB PS representative, and a biostatistician. Safety related decisions must be made with the agreement of at least the external expert, the UCB study physician, and the UCB PS representative. Decisions involving reductions in dose regimen must also have the agreement of the UCB statistician and UCB pharmacometrician.

For the sequential adaptive design in this study, at least 11 interim analyses will be performed. Safety data from the interim analyses will be reviewed by the DMC to monitor the safety, to adapt the dose regimen, and to decide when and if the UCB7665 7mg/kg weekly group (Dose Arm 2), UCB7665 10mg/kg weekly group (Dose Arm 3), UCB7665 15mg/kg group (Dose Arm 4) and UCB7665 20mg/kg group (Dose Arm 5) should be opened. Planned dosing may be discontinued for all subjects in a dose arm (see Section 6.5).

The first interim analysis will be conducted after 3 subjects (receiving 5x4mg/kg) have attended the second visit of the Observation Period (ie, 7 days after final dosing). Based on this analysis, the safety of UCB7665 will be assessed by the DMC. The DMC can either recommend to continue the study as planned, to reduce the number of sc infusions (eg. to 3), or to stop the study. If the number of infusions will be reduced, the subjects in the study already treated with the IMP will receive the reduced number of infusions. Subjects enrolled after the decision of the DMC will receive the reduced number of infusions. There will be no substitution of the subject with the original number of infusions; thus, the total number of subjects will not be increased.

If the study continues without modifications, the next interim analysis will take place after data from 3 additional subjects are available. Based on the available combined data of the first 6 subjects, the DMC will decide if the 3x7mg/kg dose arm can be initiated. If the new dose arm will be initiated and if the 5x4mg/kg will be continued, new subjects will be randomly assigned to 1 of the 2 dose arms in an allocation ratio of 1:1.

If the decision is to open the 3x7mg/kg dose arm, the third interim analysis will be performed The fourth planned interim and the second visit of the Observation Period arm.

The fourth planned interim and the second visit of the Observation Period the DMC might recommend reducing the number of sc infusions in the UCB7665 7mg/kg dose arm. (ie. 7 days after final dosing). The safety of UCB7665 will be assessed by the DMC. In addition,

The fourth planned interim analysis and review of data by DMC will take place after safety data (7 days after final dose) is available for the first 6 subjects in Dose Arm 2.

All subsequent DMC meetings will be dependent on opening of Dose Arms 3, 4 and 5 and decisions of the previous DMC meetings. Review of data will occur after every 3 subjects. More details are included in the DMC charter.

During the first three interim analyses, recruitment in the Dose Arms 1 and 2 will not be stopped. If needed, subsequent DMC meetings may take place and the frequency will be detailed in the DMC charter.

The DMC will monitor data for all reported AEs, clinical findings, including vital signs (pulse rate, blood pressure, temperature, and respiratory rate) and safety laboratory values, and immunogenicity data. Pharmacokinetic data will not be required for DMC review as blood sampling will be performed at a single time point per visit only. Thus, PK data are restricted only to the concentration data and can therefore make no plausible contribution to the assessment of safety in this particular study.

Ad hoc DMC meetings can be held for other reasons if determined appropriate by the sponsor and/or external expert.

The deliberations and decisions of the DMC will be formally minuted/documented.

A detailed description of the DMC composition, processes and responsibilities, criteria to escalate to the next dose arm, and criteria to stop, or continue a dose arm will be provided in a separate DMC charter.

The analyses will be described in a separate interim SAP and will include all safety data specified in the DMC charter, which is available at the time. For the interim analyses the data, subject to analysis, should be as clean as possible; however, the database will not be locked and a snapshot will be taken.

